# Criteria for Termination of the Trial

If there is a high probability that the posterior probability of DLT at the lowest dose is more than 10% greater than the target DLT rate, indicating that the lowest dose level is too toxic, the model will recommend the early termination of the trial. If this happens, the Trial Management Group and Trial

Steering Committee will be alerted and the latter, with support of any external evidence, will recommend if the trial should be stopped.

The TSC will be allowed to declare the MTD before the full recruitment of 34 patients is completed if 12 patients have already been allocated at the most current MTD, which would be the recommended dose level for the next cohort if the trial continues.

The performance of the proposed CRM design with 33 patients was assessed via simulations in terms of accuracy of selecting the true MTD, optimal allocation, and average percentage of patients being treated at an overdose. The design was found to perform well in various scenarios. More details of the operating characteristics of the proposed CRM design described above will be made available in the PHAZAR Statistical Analysis Plan.

# **12.2 Definition of Outcome Measures**

#### 12.2.1 Interventional Component

#### **12.2.1.1 Primary outcome measures**

MTD of ruxolitinib in combination with 5-azacitidine in patients with advanced phase MPNs as defined by the number of reported DLTs (as defined in section 2.2) occurring within the first cycle of treatment (first 28 days).

Safety of ruxolitinib in combination with 5-azacitidine will be assessed using the CTCAE v4.0 criteria.

#### 12.2.1.2 Secondary outcome measures

The following will be analysed for patients in the interventional component:

- Best response following 3 and 6 cycles of treatment. Response will be assessed according to the following criteria:
  - Proposed criteria for response assessment in patients treated in clinical trials for MPNs in blast phase (MPN-BP): Formal recommendations from the post-MPN acute myeloid leukaemia consortium" (for patients with ≥20% bone marrow blasts at baseline)[1]
  - International Working Group (IWG) response criteria in myelodysplasia (for patients with <20% bone marrow blasts at baseline)[2]

In order to assess disease response, bone marrow, peripheral blood and spleen/liver assessments should be performed during days 22-25 of cycle 3 and cycle 6.

• Achievement of RBC transfusion independence after completion of cycles 3 and 6 compared to baseline.

RBC transfusion dependence is defined as transfusion of  $\geq 2$  RBC units in the 8 weeks prior to registration at baseline, and as transfusion of  $\geq 2$  RBC units in the 8 weeks prior to cycle 3-day 28 or cycle 6-day 28 for subsequent assessments.

• Achievement of platelet transfusion independence after completion of cycles 3 and 6 compared to baseline.

Platelet transfusion dependence is defined as transfusion of  $\geq 1$  platelet units in the 4 weeks prior to registration at baseline, and as transfusion of  $\geq 1$  platelet units in the 4 weeks prior to cycle 3-day 28 or cycle 6-day 28 for subsequent assessments.

- Change in the proportion of RBC or platelet transfusion-dependent patients after completion of cycles 3 and 6 compared to baseline as defined above.
- Change in palpable splenomegaly or hepatomegaly after completion of cycles 3 and 6 compared to baseline

Size of palpable spleens will be measured below the left costal margin and reported in cm Size of palpable livers will be measured below the right costal margin and reported in cm

- Duration of Complete Response (CR) or Partial Response (PR) according to established criteria
   [1] [2]
- 12 months Progression-free survival (PFS)
- 12 months Leukaemia-free survival (LFS)

- 12 months Overall survival (OS)
- Duration of trial treatment
- Mean change in haemoglobin level from baseline to end of cycles 3 and 6 (cycle 3-day 22-25 or cycle 6-day 22-25)
- Mean change in platelet count from baseline to end of cycles 3 and 6 6 (cycle 3-day 22-25 or cycle 6-day 22-25)
- Quality of life as measured by the MPN SAF; EQ-5D-5L and EORTC QLQ-C30 (at beginning of cycles 1, 2, 4 and 6)

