# 1. BACKGROUND AND RATIONALE

# 1.1 Background

Blast phase myeloproliferative neoplasm (MPN-BP) has a dismal prognosis with non-transplant therapy. Therapeutic options are limited and may include supportive care only, low dose chemotherapy or conventional acute myeloid leukaemia (AML)-type induction therapy. Even with the latter, remission rates are <50%[3] and responses are not durable; median survival was 6 months with intensive induction therapy in one study and all patients were projected to have died from their disease by 3 years. Furthermore, these poor results were near identical to those achieved with a low-dose chemotherapy approach [3]. While stem cell transplant may be associated with long-term survival, the advanced median age of this patient group (64 years and 68.5 years in two large cohorts respectively [3, 4]) precludes this as a treatment for most patients.

JAK2 inhibitors are now licensed and approved for use in Myelofibrosis (MF), with treatment shown to reduce spleen size, improve symptoms and, tantalizingly, perhaps increase survival (reviewed in [5]), and for polycythaemia vera resistant/intolerant to hydroxyurea. There is little published data however, on their use in advanced phase MPNs. A recent study documented a 16% CR rate (3 of 18 patients) with AML secondary to preceding MPN treated with ruxolitinib, using a large starting dose of 25 mg BD[6]. Haematological toxicity was modest and the drug was well tolerated, allowing for continued therapy of responders. This modest (although encouraging) activity as well as its good tolerability suggests that it would be a useful component of any combination strategy.

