# **12.3 Analysis of Outcome Measures**

Descriptive statistics will be reported for all patients recruited as described below.

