#### Interventional component

Primary outcome measure

• The MTD, defined as the dose level with an associated DLT probability over the first cycle of treatment (28 days) closest to the target DLT rate of 25%, will be reported with its associated probability of DLT and 90% probability interval.

Secondary outcome measures

- Best response following 3 and 6 cycles of treatment will be reported as the number and proportion of patients in each response category and overall.
- DLTs and AEs (according to the CTCAE criteria version 4.0), records of blood and platelet transfusions, physical examinations to assess spleen and liver size, blood counts (including haemoglobin and platelet count, quality of life questionnaires and survival data) will be collected and reported in a descriptive manner.

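### The net change in the proportion transfusion-dependent cannot separate patients who improved from patients who died or stopped

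*Protocol*

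**What the plan says.** Protocol section 12.2.1.2 lists three kinds of transfusion outcome for the interventional component.

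- Two are patient-level: "Achievement of RBC transfusion independence after completion of cycles 3 and 6 compared to baseline", and the same for platelets.
- The third is a net change: "Change in the proportion of RBC or platelet transfusion-dependent patients after completion of cycles 3 and 6 compared to baseline as defined above".

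Status is set by a unit count. For red cells, "RBC transfusion dependence is defined as transfusion of" at least 2 units in the 8 weeks before registration, and afterwards at least 2 "RBC units in the 8 weeks prior to cycle 3-day 28 or cycle 6-day 28 for subsequent assessments". For platelets it is at least 1 unit in the 4 weeks before registration, and afterwards at least 1 of the "platelet units in the 4 weeks prior to cycle 3-day 28 or cycle 6-day 28 for subsequent assessments". Neither definition requires the patient to be alive or on study through the window.

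Section 12.3 opens with "Descriptive statistics will be reported for all patients recruited as described below" and then lists "records of blood and platelet transfusions, physical examinations to assess spleen and liver size" among the data to be reported descriptively. It gives no denominator for the transfusion outcomes and no category for patients who die or stop before cycle 3 day 28 or cycle 6 day 28. Twelve-month overall survival is a separate secondary outcome. Section 7.5.9 has every transfusion recorded from 8 weeks before registration to the end of the study.

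**The concern.** A net change in a proportion has two sources: patients who change status, and patients who leave the group being counted. In a population with high early mortality the second can be as large as the first.

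The protocol's wording allows at least two denominators. One is everyone recruited, following the opening sentence of section 12.3. There, a patient who died before the window opened has received no units and so falls below the threshold. The other is the patients who completed cycle 3 or cycle 6, so that the baseline and later proportions describe different people.

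Clinical activity is a secondary objective, and section 12.4 has the management and steering committees look at activity as well as safety data at the interim assessment. A reported fall in dependence could then be taken as activity when part or all of it is attrition.

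**Working it through.** The protocol gives no figure for this outcome, so there is none to reproduce. The check asks how far the proportion moves when **no surviving patient changes transfusion status**.

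**Inputs from the protocol**
- Maximum of 34 interventional patients (synopsis).
- 28-day cycles, so cycle 3 day 28 is day 84 and cycle 6 day 28 is day 168 if no cycle is delayed. Section 7.8.2 allows delays, which would move the assessments later.
- Section 1.1: "median survival was 6 months with intensive induction therapy in one study".

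**Assumptions**
- Exponential survival with that median applies to this trial.
- 60% of patients are dependent at baseline (not stated in the protocol).
- The ratio of death hazards, dependent to independent, ranges from 2/3 to 2 (not stated in the protocol).

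**Step 1: mortality.** Six months × 30.44 days = 182.6 days, and S(t) = 0.5^(t/182.6).
- Day 84: S = 0.727, so 27% dead, about 9 of 34.
- Day 168: S = 0.529, so 47% dead, about 16 of 34.

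**Step 2: all recruited, equal mortality.**
- Dead counted as not dependent: 0.60 × 0.727 = 44% and 0.60 × 0.529 = 32%.
- Dead counted as dependent: 0.436 + 0.273 = 71% and 0.317 + 0.471 = 79%.
- With a 9-month median, dead counted as not dependent: S = 0.809 and 0.654, giving 49% and 39%.

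A purely literal unit count is slightly milder than the first line, because a patient who dies inside the window after reaching the threshold still counts as dependent. Only deaths before the window opens are certain to score zero. For red cells the windows open on day 28 and day 112. S = 0.899 and 0.654 there, so the literal figure lies between 44% and 54% at cycle 3 and between 32% and 39% at cycle 6.

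**Step 3: survivors only.** Let h be the monthly hazard in independent patients and r × h that in dependent patients. Choose h so that overall median survival stays at 6 months: 0.6·exp(−6rh) + 0.4·exp(−6h) = 0.5. The proportion dependent among survivors at t months (2.76 and 5.52) is 0.6·exp(−rht) / [0.6·exp(−rht) + 0.4·exp(−ht)].

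| r | h | cycle 3 | cycle 6 |
|---|---|---|---|
| 2/3 | 0.1465 | 63% | 66% |
| 1 | 0.1155 | 60% | 60% |
| 1.5 | 0.0900 | 57% | 54% |
| 2 | 0.0748 | 55% | 50% |

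**Step 4: whole-number example at cycle 6.** Suppose 20 of 34 (59%) are dependent at baseline, 12 dependent and 4 independent patients die, and nobody else changes. The same data give 8/18 = 44% among survivors, 8/34 = 24% with the dead as not dependent, and 24/34 = 71% with the dead as dependent. The direction of the result depends on a rule that the protocol does not state.

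**The case against.** **The protocol is silent; it does not exclude deaths.** A reader might infer that deaths are left out or scored as non-dependent. No sentence says so. Denominators and the handling of early deaths are commonly set in a statistical analysis plan, and section 12.1 refers to one, which was not available here. This stands: silence alone is no error. What remains is that the protocol itself chose the net change, and a denominator rule alone does not make a net change show who improved.

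**The bias does not always favour benefit.** That inference is tempting but wrong. As step 3 shows, survivors give no change under equal mortality and a rise if independent patients die faster. A fall is certain only when the dead stay in the denominator as non-dependent, and the words about completing cycles 3 and 6 point away from that reading.

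**Within-patient outcomes already exist.** Achievement of independence is listed separately for red cells and platelets, and mortality alone does not create an achieved independence unless a dead patient is scored independent. This stands, and it narrows the point to the net-change outcome plus the denominator of the other two.

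**Within-patient analysis has its own weakness.** Patients selected as dependent at baseline regress to the mean. With an unchanged Poisson need of 3 red-cell units per 8 weeks, P(0 or 1 unit) = e^−3 × (1 + 3) = 20% would look independent later by chance. The net change has no such drift in expectation, because the threshold is the same at both times. This stands, so movement in both directions has to be shown.

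**The thresholds are not a fault.** One may be tempted to object that a patient receiving 1 red-cell unit counts as independent while 1 platelet unit counts as dependence. Both are explicit, and each is the same at baseline and follow-up. A different threshold would be a preference.

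**Importance.** Nothing in the protocol makes this a main activity signal. It is one of many secondary outcomes and is reported descriptively.

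**Conclusion.** The point holds in a limited form. The net change in the proportion dependent mixes improvement with death and drop-out, and its size and even its sign depend on how patients who die are classified. With no patient improving, a 60% baseline proportion could be reported at cycle 6 as about 32% (all recruited, dead not dependent), 50% to 66% (survivors, hazard ratio 2 down to 2/3) or 79% (all recruited, dead dependent).

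These figures illustrate; they do not predict. The 6-month median comes from an external blast-phase cohort on intensive therapy, and this trial also enrols accelerated-phase patients, so mortality may be lower. Baseline dependence and the hazard ratios are assumed. No dose rule, error rate or sample size rests on this outcome. Minor priority.

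**What to change.** 1. Replace the net change with a shift table, separately for red cells and platelets. Rows give baseline status; columns give status at cycle 3 and at cycle 6 as dependent, independent, or dead/off study. Include all treated patients.
2. For the two existing independence outcomes, state the denominator as patients dependent at baseline, and count death or discontinuation before the assessment as not independent.
3. Alongside, report the proportion of baseline-independent patients who become dependent or die, so that regression to the mean and deterioration are visible.
4. Leave the unit thresholds and windows as they are.

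The cost is a few sentences and one table. The transfusion records required by section 7.5.9 and the survival follow-up already supply the data. The downside is that the reported improvement may look smaller.

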#### Secondary

- Best response following 3 and 6 cycles of treatment
  - Assessment will be made according to the following criteria:
    - "Proposed criteria for response assessment in patients treated in clinical trials for MPNs in blast phase (MPN-BP): Formal recommendations from the post-MPN acute myeloid leukaemia consortium" (for patients with ≥20% bone marrow blasts at baseline)[1]
    - International Working Group (IWG) response criteria in myelodysplasia (for patients with <20% bone marrow blasts at baseline)[2]

- Change in the proportion of patients who require transfusion of red cells or platelets after completion of cycles 3 and 6
- Achievement of red blood cell (RBC) transfusion independence after completion of cycles 3 and 6.
- Achievement of platelet transfusion independence after completion of cycles 3 and 6.
- Change in palpable splenomegaly or hepatomegaly after completion of cycles 3 and 6.
- Duration of Complete Response (CR) or Partial Response (PR)
- 12 months Progression-free survival (PFS)
- 12 months Leukaemia-free survival (LFS)

- 12 months Overall survival (OS)
- Duration of trial treatment
- Clinical improvement in haemoglobin level
- Clinical improvement in platelet count
- Quality of life as measured by the MPN SAF; EQ-5D-5L and EORTC QLQ-C30 (baseline and cycles 1, 2, 4 and 6)

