#### Cytopenias

Cytopenias will not be an indication for dose delay. MPN-BP is often associated with profound peripheral cytopenia (neutropenia, thrombocytopenia or anaemia). Patients who have these features at baseline or who develop these whilst on treatment may receive supportive care in the form of red cell or platelet transfusion or growth factor support at the local Investigator's discretion.

5-azacitidine and ruxolitinib are associated with cytopenias and bone marrow suppression and dose modifications are not scheduled for these events. In the event of severe bone marrow suppression or cytopenias following acquisition of a clinical response and not considered disease related, the CI must be informed to decide an appropriate course of action. Complete blood counts will be performed as per the above schedule, and at other time-points according to investigator discretion.

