# 7.10 Supportive Treatment

#### **Interventional Component**

As ruxolitinib is associated with the development and reactivation of bacterial, fungal and viral infections, patients should be monitored for symptoms at protocol visits and use of antibiotic, antiviral and antifungal prophylaxis are advised as per local protocols. Special attention should be paid to the possibility of reactivation of tuberculosis and Herpes Zoster. Patients should be educated about the early symptoms of Herpes Zoster to enable them to notify the research team and receive treatment as soon as possible.

Patients may also receive treatment with G-CSF/GM-CSF and / or blood transfusions (red blood cells and platelets) as applicable. EPO and TPO are prohibited throughout the trial.

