#### Other prohibited concomitant medications:

Patients should not receive any chemotherapy, anticancer immunotherapy, other investigational therapy or other JAK2 inhibitors whilst on trial treatment. Cytoreductive treatment is also prohibited throughout the trial with the exception of hydroxycarbamide and anagrelide, which can be used to control blood cell counts or manage aggressive disease following consultation with the Chief Investigator for a period not exceeding 28 days. Hydroxycarbamide or anagrelide prescribed prior to study entry must be stopped before the first scheduled day of trial treatment.

Splenic irradiation is prohibited throughout the trial. Sites are requested to obtain prior CI approval via the trials office before administering any other radiotherapy treatment.

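### Clinical improvement in haemoglobin and platelets is analysed as a mean change, with no condition on recent transfusion

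*Protocol*

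**What the plan says.** The synopsis and Protocol section 2.2 list two secondary outcomes by name only: "Clinical improvement in haemoglobin level" and "Clinical improvement in platelet count". Neither place gives a threshold, a direction or a transfusion condition.

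Section 12.2 is the part of the Protocol that defines the outcome measures. There, section 12.2.1.2 lists "Mean change in haemoglobin level from baseline to end of cycles 3 and 6" and "Mean change in platelet count from baseline to end of cycles 3 and 6", each read at days 22-25 of the cycle. Section 12.3 adds that blood counts, together with transfusion records and other data, "will be collected and reported in a descriptive manner".

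On transfusion, section 7.8.2 (Cytopenias) expects profound cytopenia to be common in blast phase and lets the local investigator give "supportive care in the form of red cell or platelet transfusion or growth factor support". Section 7.10 says: "Patients may also receive treatment with G-CSF/GM-CSF and / or blood transfusions (red blood cells and platelets) as applicable". The same section prohibits EPO and TPO. Section 7.5.9 has every red cell and platelet transfusion recorded, from 8 weeks before registration to the end of the study.

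**The concern.** Improvement is something that a patient does or does not achieve. A group mean gives neither the number of patients who improved nor their identity, so the analysed variable does not answer the outcome as named.

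The mean is also exposed to transfusion at both ends. A haemoglobin or platelet value taken soon after a transfusion reflects the patient's own production plus what was transfused. A patient who starts transfusion during treatment can appear to improve. A patient who was transfused at baseline and no longer needs it loses that contribution, and may show no change or a fall although this is the favourable result.

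At stake is how two of the trial's clinical activity outcomes are read. Clinical activity of the combination is a secondary objective in section 2.1.

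**Working it through.** The Protocol gives no effect size, standard deviation, power or test for these outcomes, so there is no figure to reproduce. The check sets the passages side by side and then shows, on stated assumptions, how far the mean can move.

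**Comparison of the passages**

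| Item | Protocol |
|---|---|
| Outcome as named | Clinical improvement (synopsis, section 2.2) |
| Outcome as analysed | Mean change from baseline to days 22-25 of cycles 3 and 6 (section 12.2.1.2) |
| Transfusion condition on the value | None stated |
| Transfusion windows elsewhere in section 12.2.1.2 | 8 weeks (red cells) and 4 weeks (platelets), used only for transfusion dependence and independence |
| Transfusion data | All transfusions from 8 weeks before registration (section 7.5.9) |
| Maximum number of patients | 34 (synopsis) |

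**Haemoglobin: group mean with no true change**

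Let L be the lift in a reading from a recent transfusion, and d the change in the proportion of patients recently transfused between baseline and the assessment. Both are assumptions.

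Spurious mean change = L × d

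- Smallest case: 5 g/L × 0.20 = 1 g/L.
- Largest case: 20 g/L × 0.40 = 8 g/L.

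The sign follows d. More transfusion at the assessment pushes the mean up, and less pushes it down.

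**Haemoglobin: a patient who stops needing transfusion**

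Observed change = true rise − lift lost

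- True rise 10 g/L, lift lost 10 g/L: 10 − 10 = 0.
- True rise 10 g/L, lift lost 20 g/L: 10 − 20 = −10 g/L.
- True rise 15 g/L, lift lost 10 g/L: 15 − 10 = +5 g/L.
- True rise 15 g/L, lift lost 20 g/L: 15 − 20 = −5 g/L.

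**Platelets: opposite favourable movements (illustration only)**

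High baseline counts are possible. Patients with prior ET, PV or MF are eligible, and section 4 sets no platelet limit. Section 7.11 allows short use of hydroxycarbamide or anagrelide, "which can be used to control blood cell counts or manage aggressive disease following consultation with the Chief Investigator". Suppose k of 34 patients start high and fall by 250 × 10⁹/L while the others start low and rise by 50 × 10⁹/L, both taken as favourable.

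Mean change = [(34 − k) × 50 + k × (−250)] / 34

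- k = 0: +50.0
- k = 4: (1500 − 1000)/34 = +14.7
- k = 6: (1400 − 1500)/34 = −2.9
- k = 8: (1300 − 2000)/34 = −20.6

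The mean is zero when the high-count fraction equals rise/(rise + fall) = 50/300 = 16.7%, or 5.7 of 34 patients. With other assumed movements:

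- +30 and −250: 30/280 = 10.7%, or 3.6 of 34.
- +50 and −400: 50/450 = 11.1%, or 3.8 of 34.
- +50 and −100: 50/150 = 33.3%, or 11.3 of 34.

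The zero point thus runs from about 4 to about 11 patients on assumptions alone.

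**The case against.** The strongest reply is that section 2.2 only names the outcome and section 12.2 is where it is defined. On that view no responder definition has been displaced: a label and a definition differ, and rewording could align them. It is correct that section 2.2 defines nothing. But changing the label to mean change would leave a variable that partly records transfusion.

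Second, transfusion-aware, patient-level information is already planned. Section 12.2.1.2 has red cell and platelet transfusion independence as separate outcomes, section 12.3 reports transfusion records, and the Appendix 1 response criteria contain haemoglobin and platelet levels. EPO and TPO are prohibited. This softens the problem, since a reader need not judge benefit from the mean alone. It does not repair it, because none of these items is linked to the mean-change outcomes.

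Third, handling rules may be left to a SAP. That is fair for missing values and deaths. A reader might infer that the mean uses survivors only, but the Protocol does not say how such patients are handled, and its silence is not an error. The choice of a mean change as the analysed variable, however, is fixed in the Protocol.

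Three other strong readings go too far:

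- That platelet movements will cancel. There is no baseline platelet distribution. The Protocol's general statement on counts points to cytopenia, section 7.11 speaks of blood cell counts generally and limits the two drugs to 28 days, and either drug, if prescribed before entry, must be stopped before trial treatment starts.
- That transfusion is unrestricted. It is at the investigator's discretion.
- That a misleading mean could shift the declared MTD, because section 12.4 has the committees consider activity data at the interim assessment. The MTD is defined by the DLT rate, and no dose or MTD rule names these counts.

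**Conclusion.** The point holds in a limited form. Section 12.2.1.2 fixes a group mean change for outcomes named elsewhere as clinical improvement, without regard to recent transfusion at baseline or at the assessment. Followed as written, the mean can rise from transfusion alone, stay flat or fall when patients stop needing it, and it cannot show how many patients improved.

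The haemoglobin distortion of 1 to 8 g/L rests entirely on the assumed lift and the assumed shift in transfusion use; the Protocol supplies neither. Platelet cancellation is a possibility only. Because the outcomes are secondary and descriptive, and the MTD rule, the CRM and the sample size do not use them, this is a correction that should be made but does not threaten the primary result.

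**What to change.** In section 12.2.1.2, reconcile the two definitions with the synopsis and section 2.2:

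- Report the number and proportion of patients with improvement in haemoglobin and in platelets at cycles 3 and 6, against a threshold that the trial team fixes in advance. Appendix 1 already contains levels to consider: haemoglobin above 10 g/dL and platelets above 100 × 10⁹/L in the blast-phase criteria, and at least 11 g/dL and at least 100 × 10⁹/L in the IWG criteria. State the denominator, including how patients already beyond the threshold at baseline are shown.
- Count a value as improved only if the patient had no red cell transfusion in the 8 weeks, or no platelet transfusion in the 4 weeks, before that days 22-25 sample. State that these windows end at the sample, because the existing independence windows end at day 28. State also that the red cell condition is stricter than the existing definition of dependence (2 or more units): one unit would be enough to count as not improved.
- Count patients who died, withdrew or were transfused within the window as not improved.
- Keep mean change as a supplementary description, shown by transfusion status at baseline and at the assessment, and for platelets by low or high baseline, with the number of patients contributing.

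The cost is wording and some programming, since section 7.5.9 already collects the transfusion data. The downside is small denominators: with at most 34 patients, some subgroups will hold only a few, and the proportions will be imprecise.
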